10.4.1 Reporting of an Adverse Event

All AEs will be reported on the AE page of the CRF by the investigator or site staff. It should be noted that the form for collection of SAE information is not the same as the AE CRF. Where the same data are collected, the AE CRF page and the SAE form must be completed in a consistent manner. For example, the same AE term should be used on both. AEs should be reported using concise medical terminology on the CRF as well as on the form for collection of SAE information.

10.4.2 Reporting of a Serious Adverse Event

In addition to recording the details of each AE on the AE CRF page, an SAE form should be completed, as fully as possible. Hard copies of the 'paper' SAE form will be provided in the investigator study master file. Original SAE forms will be retained in the investigator study master file.

It is essential to enter the following information:

- Protocol and subject identifiers
- Subject demography
- Description of events, with diagnosis if available
- Investigator opinion of relationship to study product (or study procedure, if appropriate)
- Criterion for seriousness.

The following are desirable and are of particular relevance for investigator and the sponsor assessment of the SAE report:

- Date of onset of AE
- Date AE stopped, if relevant
- Study product start date
- Study product end date if relevant
- Action taken in relation to the study product
- Outcome if known

The SAE form, completed as fully as possible, must be scanned and e-mailed to the Case Management Group mailbox ([PPD](#)), with copy to the appropriate CH Study Manager, with the study number and subject number in the subject line of the email **immediately and under no circumstance should this exceed 24 hours** after study site personnel learn of the event. The investigator will submit any updated SAE data to the sponsor, **immediately and under no circumstance should this exceed 24 hours** of it being available.

The initial report will be followed up with more information as relevant, or as requested by the CH study manager.

The CH Study Manager will be responsible for forwarding the SAE form to other CH personnel as appropriate.

10.5 Evaluating Adverse Events

10.5.1 Assessment of Intensity

The investigator or medically qualified designee will make an assessment of intensity for each AE reported during the study and will assign it to one of the following categories:

- Mild: An event that is easily tolerated by the subject, causing minimal discomfort and not interfering with everyday activities.
- Moderate: An event that is sufficiently discomforting to interfere with normal everyday activities
- Severe: An event that prevents normal everyday activities.

NOTE: An AE that is assessed as severe should not be confused with an SAE. Severe is a category utilized for rating the intensity of an event; and both non-serious AEs and SAEs can be assessed as severe. For example, a headache may be severe (interferes significantly with the subject's usual function) but would not be classified as serious unless it met one of the criteria for SAEs, listed above. An event is defined as 'serious' when it meets at least 1 of the predefined outcomes as described in the definition of an SAE, NOT when it is rated as severe.

10.5.2 Assessment of Causality

The causality assessment is one of the criteria used when determining regulatory reporting requirements.

For each AE (serious and non-serious), the investigator (or medically qualified designee) **must** provide an assessment of causality on the AE CRF page and the SAE form (subject to the classification of the AE). The investigator will also document in the medical notes that they have reviewed the AE and assessed causality, where applicable.

A "reasonable possibility" of a relationship conveys that there are facts, evidence, and/or arguments to suggest a causal relationship, rather than a relationship cannot be ruled out. Generally, the facts (evidence) or arguments to suggest a causal relationship should be provided.

The investigator will use clinical judgment to determine the relationship and will also consult the Safety Statement, in the determination of their assessment. Alternative causes, such as underlying disease(s), concomitant therapy, other risk factors, and the temporal relationship of the event to the study product will be considered and investigated.

For each AE/SAE, the investigator must document in the medical notes that they have reviewed the AE/SAE and has provided an assessment of causality.

The investigator's assessment of causality must be provided for all AEs (serious and non-serious); the investigator must record the causal relationship in the CRF, as appropriate, and report such an assessment in accordance with the SAE reporting requirements if applicable.

There may be situations when an SAE has occurred, and the investigator has minimal information to include in the initial report to the sponsor. **However, it is very important that the investigator always make an assessment of causality for every event prior to the initial transmission of the SAE data to the sponsor.** The investigator may change their opinion of causality in light of follow-up information and send an SAE follow-up report with the updated causality assessment.

10.6 Follow-up of AEs and SAEs

After the initial AE/SAE report, the investigator is required to proactively follow up with each subject and provide further information on the subject's condition.

All AEs (serious and non-serious) will be followed until resolution, until the condition stabilizes, until the event is otherwise explained, or until the subject is lost to follow-up.

The investigator is obligated to perform or arrange for the conduct of supplemental measurements and/or evaluations as may be indicated or as requested by the sponsor to elucidate as fully as possible the nature and/or causality of the AE. This may include additional laboratory tests or investigations, histopathological examinations, or consultation with other health care professionals.

New or updated information will be recorded on the AE CRF page and on the SAE form (subject to the classification of the AE).

The investigator will submit any updated SAE data to the sponsor within 24 hours of receipt of the information.

Investigators are not obliged to actively seek AEs in former subjects. However, if the investigator learns of a SAE, including death, at any time after a subject has been discharged from the study, and considers the event reasonably related to the study product or study participation, the investigator will promptly notify the sponsor by emailing the information to the Case Management Group mailbox at (PPD [REDACTED]), with copy to the appropriate CH Study Manager.

The investigator will submit any updated SAE data to the sponsor within the designated reporting time frames.

10.7 Withdrawal Due to an Adverse Event

Withdrawal due to AEs should be distinguished from withdrawal due to other causes, according to the definition of an AE noted earlier, and recorded on the appropriate AE CRF page.

When a subject withdraws because of an SAE, the SAE must be reported in accordance with the reporting requirements defined.

10.8 Regulatory Reporting Requirements for SAEs

The sponsor has a legal responsibility to notify, as appropriate, the local regulatory authority and other regulatory authorities about the safety of a product under clinical investigation.

Property of GSK Consumer Healthcare - Confidential

May not be used, divulged, published or otherwise disclosed without the consent of GSKCH

Prompt notification of SAEs by the investigator to the sponsor is essential so that legal obligations and ethical responsibilities towards the safety of subjects are met.

The sponsor will comply with country specific regulatory requirements relating to safety reporting to the regulatory authority, IRB/EC and investigators.

Both the investigator and the sponsor will comply with all local medical device reporting requirements

Investigator safety reports must be prepared for suspected unexpected serious adverse reactions (SUSAR) according to local regulatory requirements and sponsor policy and forwarded to investigators as necessary.

An investigator who receives an investigator safety report describing a SAE or other specific safety information e.g. summary or listing of SAE from the sponsor will review and then file it along with the Safety Statement in the investigator study master file, and will notify the IRB/IEC, if appropriate according to local requirements.

10.9 Pregnancy

10.9.1 Time Period for Collecting Pregnancy Information

Pregnancy information will be collected on all pregnancies reported while a female subject is participating in the study from the signing of informed consent until 5 days after last administration of study product.

10.9.2 Action to be Taken if Pregnancy Occurs

The investigator will record pregnancy information on the appropriate form scan and e-mail it to the Case Management Group mailbox (PPD [REDACTED]), with copy to the appropriate CH Study Manager. Original pregnancy information forms will be retained in the investigator study master file.

The subject will be followed to determine the outcome of the pregnancy. Information on the status of the mother and infant / neonate (including concomitant medications taken by the mother during the pregnancy) will be forwarded by the investigator to the Case Management Group mailbox at (PPD [REDACTED]), with copy to the appropriate CH Study Manager. Generally, follow-up will be no longer than 6 to 8 weeks following the estimated delivery date. Any termination of the pregnancy will be reported.

While pregnancy itself is not considered to be an AE, abnormal pregnancy outcomes (e.g. spontaneous abortion, fetal death, stillbirth, congenital anomalies, ectopic pregnancy) are, and should be recorded as an SAE.

Any female subject who becomes pregnant while participating will be withdrawn from the study.

10.10 Medical Device Incidents

Both the investigator and the sponsor will comply with all local medical device reporting requirements.

Medical devices are being provided by the sponsor for use in this study; the medical device in this study is the supplied toothbrush.

10.10.1 Definition of an Incident

A medical device incident is any malfunction or deterioration in the characteristics and/or performance of a device as well as any inadequacy in the labeling or the instructions for use which, directly or indirectly, might lead to or might have led to the death of a subject/user/other person or to a serious deterioration in their state of health.

Not all incidents lead to death or serious deterioration in health. The nonoccurrence of such a result might have been due to other fortunate circumstances or to the intervention of health care personnel.

It is sufficient that:

An **incident** associated with a device happened and

- The **incident** was such that, if it occurred again, might lead to death or a serious deterioration in health.
- A serious deterioration in state of health can include any of the following:
 - Life-threatening illness
 - Permanent impairment of body function or permanent damage to body structure
 - Condition necessitating medical or surgical intervention to prevent one of the above
 - Fetal distress, fetal death, or any congenital abnormality or birth defects

Examples of incidents:

- A subject, user, caregiver, or healthcare professional is injured as a result of a medical device failure or its misuse.
- A subject's study treatment is interrupted or compromised by a medical device failure.
- A misdiagnosis due to medical device failure leads to inappropriate treatment.
- A subject's health deteriorates due to medical device failure.

10.11 Reporting of Incidents and Malfunctions

All incidents must be reported to the sponsor **immediately and under no circumstance should this exceed 24 hours** of the investigator or designee becoming aware of the situation.

Any medical device incident occurring during the study will be documented in the subject's medical records, if in accordance with the investigator's normal clinical practice, and on the appropriate Incident Report Form. In addition, for incidents fulfilling the definition of an AE (serious and non-serious), the appropriate AE CRF page and SAE form will be completed and reported as per the AE and SAE reporting sections.

The Incident Report Form will be completed as thoroughly as possible and signed by the investigator before transmittal to the sponsor. It is very important that the investigator describes any corrective or remedial actions taken to prevent recurrence of the incident.

The completed Incident Report Form should be scanned and emailed to the Case Management Group mailbox (PPD [REDACTED]), with copy to the appropriate CH Study Manager, with the study number and subject number in the subject line of the email **immediately and under no circumstance should this exceed 24 hours** after study site personnel learn of the event. If there is an SAE, the completed SAE form should be sent together with this report form. However, if a copy of the SAE report is sent with this form, this does not

replace the procedure to report an SAE. The original Incident Report Form will be retained in the investigator study master file.

The initial report will be followed up with more information as relevant, or as requested by the CH study manager.

The investigator will follow the following directions regarding the reporting of a device failure (malfunction):

- Notify the sponsor immediately (by following the process described above).
- Schedule the subject to return to the site promptly to return the failed device.
- Record any incidents on the CRF and Incident Report Form following instructions given in the section above.
- For any incident/malfunction occurring with a medical device (including those that are part of combination products) supplied by the sponsor, return the failed device to the sponsor as soon as possible, including documentation of the details of the failure.
- For any incident/malfunction occurring with a medical device (including those that are part of combination products) supplied by the Investigator site, report the incident to the device manufacturer and follow the manufacturer instructions for the return of the failed device (whilst keeping the sponsor informed).

10.12 Follow-up of Medical Device Incidents

Medical device incidents involving an AE will be followed and reported in the same manner as other AEs. This applies to all subjects, including those who discontinue study product or are withdrawn from the study.

The investigator is responsible for ensuring that follow-up includes any supplemental investigations as indicated to elucidate the nature and/or causality of the incident.

New or updated information will be recorded on the originally completed Incident Report form with all changes signed and dated by the investigator.

10.13 Regulatory Reporting Requirements for Medical Device Incidents

To fulfill regulatory reporting obligations worldwide, the investigator is responsible for the detection and documentation of events meeting the definitions of incident or malfunction that occur during all periods of the study in which the medical device is used.

The investigator will promptly report all incidents occurring with any medical device provided for use in the study in order for the sponsor to fulfill the legal responsibility to notify appropriate regulatory authorities and other entities about certain safety information relating to medical devices being used in clinical studies.

The investigator, or responsible person according to local requirements (e.g. the head of the medical institution), will comply with the applicable local regulatory requirements relating to the reporting of incidents to the IRB/IEC.

11 DATA MANAGEMENT

As used in this protocol, the term CRF is understood to refer to either a paper form or an electronic data record or both, depending on the data collection method.

For this study, subject data will be entered into an electronic CRF (eCRF), using a validated system. Data relating to SAEs, pregnancy and incidents will also be collected on paper forms.

The investigator is responsible for verifying that data entries are accurate and correct by physically or electronically signing the CRF.

The source documents (e.g. hospital records, clinical and office charts, laboratory notes, memoranda, subject diaries, questionnaires, evaluation checklists, pharmacy dispensing records, recorded data from automated instruments, microfiches, photographic negatives, microfilm or magnetic media, x-rays, subject files and records kept at the pharmacy, at the laboratory and at the medico-technical departments involved in the clinical study) which contain the source of data recorded in the CRF should be specified. The CRF and or diary can be used as a source document at the discretion of data management.

Each subject will be assigned and identified by a unique Screening Subject Number. Any reference made to an individual subject within the study must be done using their unique Screening Subject Number.

11.1 Case Report Form

A CRF is a printed, optical, or electronic document designed to record the protocol required information to be reported to the sponsor on each trial subject.

For each subject who has given informed consent/assent the CRF must be completed and signed by the Principal Investigator (or authorized designee) to certify that the data are complete and correct. The investigator must maintain accurate documentation (source data) that supports the information entered in the CRF.

Management of clinical data will be performed in accordance with Third Party Vendor applicable standards and data cleaning procedures with oversight by the sponsor to ensure integrity of the data, for example, to correct errors and inconsistencies in the data.

To protect the privacy of subjects, no Personal Information (PI) (including the subject's name or initials or full birth date) is to be recorded in the CRF or as part of the query text.

All CRF pages should be completed during a subject assessment when the CRF has been designated as the source. Data that is sourced elsewhere should be entered into the CRF in an agreed upon timeframe between the Investigator and sponsor.

The sponsor will obtain and retain all CRFs and associated study data as applicable at the completion of the study.

11.2 Data Handling

Documentation of all data management activities should allow step-by-step retrospective assessment of data quality and study performance.

Any changes or corrections to data will be performed in the Electronic Data Capture (EDC) System, and it will include rationale for changes. The EDC system has an audit trail, which will provide a complete record of the changes and corrections endorsed by the Investigator.

Adverse events will be coded using Medical Dictionary for Regulatory Activities (MedDRA) and any concomitant medications terms (if applicable) using a validated medication dictionary, WHODrug.

11.2.1 Data Queries

Programmed edit checks will be generated automatically, as the data are being entered into the system. Reports and listings on the CRF data will also be run, in addition to the queries already programmed and generated by the system, to raise manual queries as needed for site clarification or correction. The sponsor's third party vendor will raise queries as needed on safety data to code the terms (AEs and Drugs or concomitant medication) appropriately.

The study monitor will perform ongoing review of the CRFs in accordance with the monitoring plan, to confirm that data entered into the CRF by authorized site personnel are accurate, complete, and verifiable from source documents; that the safety and rights of participants are being protected; and that the study is being conducted in accordance with the currently approved protocol and any other study agreements, ICH GCP, and all applicable regulatory requirements.

Any queries will be generated in the EDC System to the Investigator or designee, enabling the errors to be addressed in parallel with Data Management review. The study monitor can also run reports and listings on the CRFs, to raise manual queries as needed for site clarification or correction.

11.3 Processing Patient Reported Outcomes

Paper based patient reported outcome (PRO) data may be recorded to a diary, questionnaire, or other specified document, etc. and entered into the data management system (DMS).

All PRO source data should be reviewed by the study staff and the study monitor to ensure accurate transcription of data and that any potential AEs or concomitant medications reported on these documents are discussed with the subject and transcribed accurately to the CRF and/or DMS. PROs that are classed as source data will be retained by the investigator and true/certified copies may be sent to a designated vendor or sponsor as required.

To protect the privacy of subjects, no Personal Information (PI) (including the subject's name or initials or birth date) is to be recorded on any PRO that will be forwarded to the sponsor or Third-Party Vendor.

12 STATISTICAL CONSIDERATIONS AND DATA ANALYSES

12.1 Sample Size Determination

Sufficient subjects will be enrolled to randomize approximately 106 subjects to have at least 100 complete the study (at least 50 subjects per treatment arm). It is considered sufficient to have 100 subjects complete in this study to meet the study's objectives. The subjects will be stratified by their sex prior to randomization.

Existing GSKCH studies were referred to for information and data to enable calculation of an appropriate power and sample size however no relevant information was observed for a 3-week study in a gingivitis population as planned for this study.

Data from a published study that evaluated halitosis in subjects with gingivitis and periodontitis ([Pham et al., 2011](#)) was taken into consideration to provide information regarding the variability and sample size for this endpoint. The sample size in this literature was N=116 for the gingivitis population and the variability estimate was observed to be 0.46 for the organoleptic score. The scoring was on a 5-point scale with very similar descriptors to those to be used in this study however only one assessor was used for organoleptic score assessment (as opposed to 3

assessors which will be used in this study). Considering the number of assessors in this study, the standard deviation was estimated to be 0.265 (0.46/sqrt(3)).

Using the standard deviation of 0.265, for 50 subjects per arm (100 subjects completing the study) the detectable mean difference is estimated to be 0.15 for 80% power and alpha=0.05.

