4 STUDY DESIGN

4.1 Overall Design

This will be a single center, single blind (to the examiners undertaking the oral malodor assessments), randomized (stratified by the subject's sex), controlled, two arm parallel study in volunteers with clinically diagnosed gingivitis and oral malodor. The study will evaluate the clinical efficacy of an experimental dentifrice containing 0.454% stannous fluoride and 0.3% zinc chloride to reduce oral malodor after 3 weeks of twice-daily use compared to a regular reference dentifrice.

Potential subjects will attend a screening visit to determine their suitability to participate having abstained from oral hygiene procedures and food consumption for at least 8 hours. Having obtained their written informed consent, relevant details of their medical history and current medications will be recorded, followed by the screening assessment of their oral malodor. Subjects will then undergo oral soft tissue (OST) and oral hard tissue (OHT) examinations, and a gingivitis assessment (bleeding on probing examination). Subjects with sufficient gingivitis and sufficient concentration of hydrogen sulfide in their breath as per the inclusion criteria, as well as meeting all other study criteria, will be considered as eligible to proceed, appointed for baseline assessments and dispensed a washout dentifrice and toothbrush to use instead of their regular oral hygiene products until they return for Visit 2 (1-3 weeks after screening). A washout diary will also be dispensed for the subjects to record their washout product usage.

At the Baseline visit (Visit 2) subjects, having abstained from oral hygiene procedures and food consumption for at least 8 hours, will undergo baseline breath VSC (using the OralChroma instrument) and organoleptic assessments (judged by a panel of 3 assessors using the hedonic scale of Rosenberg ([Rosenberg et al., 1991b](#))). The organoleptic panel will have been recently calibrated and standardized (within the past year) with a kappa statistic of ≥ 0.6 per the American Dental Association guidelines ([ADA, 2016](#)).

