5.2 Inclusion Criteria

An individual must meet all the following inclusion criteria to be eligible for enrollment into, and continuance in the study:

1. Provision of a signed and dated informed consent document indicating that the subject has been informed of all pertinent aspects of the study before any assessment is performed.
2. Subject is of either sex and any gender who, at the time of screening, is between the ages of 18-65 years, inclusive.
3. Subject who is willing and able to comply with scheduled visits, product usage requirements, study procedures and lifestyle restrictions.
4. Subject in good general and mental health with, in the opinion of the investigator or medically qualified designee, no clinically significant or relevant abnormalities in medical history (for example, a medical condition or medication confirmed to contribute to xerostomia), or upon oral examination, that would impact the subject's safety, wellbeing or the outcomes of the study, if they were to participate in the study, or affect the subject's ability to understand and follow study procedures and requirements.
5. Subject with generally good oral health that fulfil all of the following:
 - a. Having at least 20 natural (vital) teeth.
 - b. Good oral health without lesions in the oral cavity (including the tongue) that could interfere with the study evaluations.
 - c. Having clinically diagnosed, plaque-induced gingivitis defined as having 10-30 % bleeding sites from the bleeding on probing assessment.
 - d. At Screening (Visit 1) and prior to brushing with assigned dentifrice at Baseline (Visit 2) subjects must provide 2 samples of mouth air, which must have a mean hydrogen sulfide concentration greater than 150ppb. There must be \leq 500ppb difference in hydrogen sulfide between the 2 samples collected at screening. Additionally, there must be \leq 500ppb difference in hydrogen sulfide between the 2 samples collected at baseline (pre-brushing).
 - e. At Baseline (Visit 2), prior to brushing with assigned dentifrice subjects must provide a breath sample with a mean organoleptic score \geq 2.

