9.2.2 Organoleptic Assessment of Oral Malodor

At each oral odor evaluation (pre- and 1 hour (± 5 minutes) post-brushing at Visits 2 and 3), the subjects will attend an odor grading station. They will place one end of a clean and sterile cylinder, about 1 3/4 inches long by 1 1/6 inches in diameter, through an opening in a privacy screen. The screen will be arranged so that the organoleptic assessors will not be able to observe the subject. Subjects will then place the cylinder in their mouth and, while the subject holds their breath, the assessors standing behind the screen will independently evaluate oral odor. During the evaluation, each subject will keep their tongue away from the palate of their mouth. Oral odor will be graded using the following scale ([Rosenberg et al., 1991b](#)):

- 0 = No appreciable odor
- 1 = Barely noticeable odor
- 2 = Slight but clearly noticeable odor
- 3 = Moderate odor
- 4 = Strong odor
- 5 = Extremely foul odor

The organoleptic assessors (using a panel of at least 3 assessors) will be blinded to the subject's product allocation and will have a minimum of a two-minute interval between individual assessments to allow adequate recovery of the assessors' olfactory senses. Wherever possible the same assessors will be used throughout the study to aid consistency of evaluation, however assessors may be replaced with another calibrated judge(s) in the event of illness or availability issues.

Prior to undergoing this assessment, subjects will be trained in the appropriate technique to ensure familiarity with the procedure requirements.

Prior to this study, the organoleptic assessors will have been recently (within the past year) calibrated and standardized with a Kappa statistic >0.6 in accordance with the American

Dentistry Association guidelines for the testing of Products Used in the Management of Oral Malodor ([ADA, 2016](#)).

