1.4 Sample Size Calculation

Sufficient subjects will be enrolled to randomize approximately 106 subjects to have at least 100 complete the study (at least 50 subjects per treatment arm). It is considered sufficient to have 100 subjects complete in this study to meet the study's objectives. The subjects will be stratified by their sex prior to randomization. Existing GSKCH studies were referred to for information and data to enable calculation of an appropriate power and sample size however no relevant information was observed for a 3-week study in a gingivitis population as planned for this study.

Data from a published study that evaluated halitosis in subjects with gingivitis and periodontitis was taken into consideration to provide information regarding the variability and sample size for this endpoint. The sample size in this literature was N=116 for the gingivitis population and the variability estimate was observed to be 0.46 for the organoleptic score. The scoring was on a 5-point scale with very similar descriptors to those to be used in this study however only one assessor was used for organoleptic score assessment (as opposed to 3 assessors which will be used in this study). Considering the number of assessors in this study, the standard deviation (SD) was estimated to be 0.265 (0.46/sqrt(3)).

Using the SD of 0.265, for 50 subjects per arm (100 subjects completing the study) the detectable mean difference is estimated to be 0.15 for 80% power and alpha=0.05.

2 Planned Analyses

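### The planning SD of 0.265 treats three assessors' scores of the same breath as uncorrelated, so the stated 0.15 at 80% power is unsupported as derived

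*Protocol*

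**What the plan says.** Protocol 12.1 reports that no suitable in-house data were found and turns to a published study of subjects with gingivitis and periodontitis. In its 116 gingivitis subjects, "the variability estimate was observed to be 0.46 for the organoleptic score". That study used one assessor and this one uses three, so the plan divides: "Considering the number of assessors in this study, the standard deviation was estimated to be 0.265 (0.46/sqrt(3". It concludes that, for 50 subjects per arm, "the detectable mean difference is estimated to be 0.15 for 80% power and alpha=0.05". The same paragraph says of the sample size: "It is considered sufficient to have 100 subjects complete in this study". SAP 1.4 repeats the derivation: "the standard deviation (SD) was estimated to be 0.265 (0.46/sqrt(3".

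Three other places in the protocol bear on it.

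- Section 4.1: "The organoleptic panel will have been recently calibrated and standardized (within the past year) with a kappa statistic of ≥ 0.6".
- Section 9.2.2, on the scoring of each subject: "the assessors standing behind the screen will independently evaluate oral odor".
- Section 12.3.1: the endpoint is the change in the mean over all recorded scores, analyzed by ANCOVA with product, gender and the baseline mean score.

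Neither document gives a between-assessor correlation or a baseline-to-Week 3 correlation. Neither says whether 0.46 is an SD of the score at one visit or of change.

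**The concern.** The variation in one assessor's scores across subjects has two parts: real differences in malodor between subjects, and assessor error. A panel of three reduces only the second. Dividing the whole SD by √3 treats all of it as error.

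The grading in Section 9.2.2 is independent in the sense that assessors do not confer, so their errors may be independent. The breath they grade is shared. If scores were uncorrelated across subjects, the panel mean would carry no information about who has more malodor. The panel must also meet a kappa threshold. Kappa is not a correlation, and the entry rule in Section 5.2 ("subjects must provide a breath sample with a mean organoleptic score" of at least 2) may lower the correlation by narrowing the sample. So no particular value is claimed here, only that zero is not credible.

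This is the only power statement for the primary endpoint and the only figure that accompanies the claim that 100 completers suffice. If the primary comparison is not significant, readers will use it to judge what the trial could have detected.

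**Working it through.** **Inputs from the documents.** One-assessor variability 0.46; three assessors; 50 completers per arm; alpha 0.05 and 80% power (Protocol 12.1); two-sided test and baseline-adjusted ANCOVA (Protocol 12.3.1).

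**Assumed, because the documents give no value.** ρ is the correlation between assessors' scores on the same subject at one visit, taken as equal for all pairs with equal assessor SDs. r is the correlation of the panel mean between baseline and Week 3.

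**1. The plan's own figure.** 0.46/√3 = 0.2656, written as 0.265. A two-sample noncentral t calculation with SD 0.265 and 50 per arm gives a detectable difference of 0.150 and power at 0.15 of 80.0%. This step is correct.

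**2. SD of a mean of three scores.** SD = 0.46 × √((1+2ρ)/3). This equals 0.46/√3 only at ρ = 0.

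**3. If 0.46 is a single-visit SD, with no gain from the covariate (r = 0):**

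| ρ | Panel SD | Detectable difference, 80% power | Power at 0.15 |
|---|---|---|---|
| 0.2 | 0.314 | 0.178 | 66% |
| 0.4 | 0.356 | 0.202 | 55% |
| 0.6 | 0.394 | 0.223 | 47% |
| 0.8 | 0.428 | 0.242 | 41% |

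**4. Same reading, with the baseline covariate.** Multiply the panel SD by √(1−r²):

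| ρ | r | Residual SD | Detectable difference | Power at 0.15 |
|---|---|---|---|---|
| 0.4 | 0.5 | 0.309 | 0.175 | 67% |
| 0.6 | 0.5 | 0.341 | 0.193 | 59% |
| 0.8 | 0.5 | 0.371 | 0.210 | 52% |
| 0.6 | 0.7 | 0.281 | 0.159 | 75% |
| 0.8 | 0.7 | 0.306 | 0.173 | 68% |
| 0.6 | 0.8 | 0.236 | 0.134 | 88% |
| 0.8 | 0.8 | 0.257 | 0.145 | 82% |

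Returning to 0.46/√3 requires (1+2ρ)(1−r²) = 1, so r = √(2ρ/(1+2ρ)). That is 0.53, 0.67, 0.74 and 0.78 at ρ = 0.2, 0.4, 0.6 and 0.8.

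There is also a ceiling on r. If assessor errors are independent between visits, only the shared true score carries over, so r cannot exceed ρ ÷ ((1+2ρ)/3) = 3ρ/(1+2ρ). That is 0.43, 0.67, 0.82 and 0.92 at the same ρ. The needed r and the ceiling meet at ρ = 0.4, so full recovery is possible only from there upward. At ρ = 0.1, 0.2 and 0.3 the best attainable SD is 0.282, 0.284 and 0.278. The detectable difference is then about 0.16 and power at 0.15 is 75%, 74% and 76%.

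**5. If 0.46 is an SD of change.** With equal variances at the two visits, ANCOVA multiplies the change SD by √((1+r)/2). The residual SD is 0.46 × √((1+2ρc)/3) × √((1+r)/2), where ρc is the between-assessor correlation of change scores. It stays at or below 0.46/√3 while ρc ≤ (1−r)/(2(1+r)), which is 0.27, 0.17 and 0.09 at r = 0.3, 0.5 and 0.7.

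To link this to the single-visit ρ, let τ be the stability of the true score between visits, with errors independent between visits. Then ρc = ρ(1−τ)/(1−ρτ) and r = 3ρτ/(1+2ρ). For τ = 0.3, 0.5 and 0.8:

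| ρ | Detectable difference | Power at 0.15 |
|---|---|---|
| 0.1 | 0.12 | 94–95% |
| 0.2 | 0.13 | 90% |
| 0.3 | 0.14 | 85–86% |
| 0.4 | 0.146–0.150 | 80–82% |
| 0.6 | 0.165–0.172 | 69–72% |
| 0.8 | 0.189–0.196 | 57–60% |

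On this reading 0.15 holds up to about ρ = 0.4 and is missed above it.

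**The case against.** The strongest reply is that 0.15 may be about right. The plan consults the source for variability of this endpoint, which is a change score, and the reference list describes the source as a trial of malodor treatment. That gives the change-SD reading some support, and step 5 shows that on it 0.15 is met or bettered for ρ up to about 0.4. The r = 0 table in step 3 is also a worst case, because the planned model adjusts for baseline; at r = 0.8, power is 88% and 82% for ρ = 0.6 and 0.8. The ceiling in step 4 assumes no persistent subject-by-assessor effects, although Section 9.2.2 keeps the same assessors where possible. Finally, the plan names no target difference, so no design goal is missed and nobody's treatment or analysis changes.

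Most of this is fair, and it limits the conclusion: the size of any loss is undetermined. It does not rescue the derivation. Neither document invokes a change SD or a covariate gain as the reason for 0.265; the only reason given is the number of assessors, and that reason is wrong. Even on the change-SD reading, dividing by √3 would need uncorrelated change scores or an offsetting covariate gain, and neither is stated.

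**Conclusion.** Wrong as written. The fault is the variance assumption behind 0.265, not the calculation from 0.265 to 0.15. The stated 80% power at 0.15 is unsupported as derived, and it is not shown to be unattainable.

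On the single-visit reading, power at 0.15 runs from 41% (ρ = 0.8, no covariate gain) to 88% (ρ = 0.6, r = 0.8) across the tabulated cases. On the change-SD reading it runs from about 57% to 95% for ρ from 0.8 down to 0.1. Every ρ, r and τ here is an assumption, and the documents do not let one choose among them. The sample size, primary test and type I error are unaffected, but the only power statement for the primary endpoint needs correcting in both documents.

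**What to change.** In Protocol 12.1 and SAP 1.4:

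1. State whether 0.46 is an SD of the score at one visit or of change.
2. Remove the division by √3 as the justification for 0.265.
3. If it is a single-visit SD, use 0.46 × √((1+2ρ)/3) × √(1−r²), label ρ and r as assumptions, and give the detectable difference for 50 per arm at 80% power as a short range with power at 0.15 beside it. Steps 3 and 4 supply the values. Leave out combinations where r exceeds 3ρ/(1+2ρ), such as ρ = 0.4 with r = 0.7, unless persistent subject-by-assessor effects are assumed and stated.
4. If it is an SD of change, define the correlation for change scores, apply √((1+r)/2), and do not carry over single-visit values of ρ.

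Once item 1 is settled, only one of items 3 and 4 is needed, and a few sentences with a small table will do. The 106 randomized, 100 completers, endpoint, model and alpha all stay. The cost is that one favorable figure becomes a range resting on stated assumptions.
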